measurement of the 6-min walking distance (6MWD). At the same time, it includes the self-measurement of 6min walking distance (6MWD), and patients can complete the self-measurement of 6MWD according to the prompts of the application;

- 6) Implementation and feedback function: It can realize the guidance and adjustment of prehabilitation strategy after reassessment; and set up functions such as daily reminder and prehabilitation activity record.

3.2 To conduct a study on the impact of short-term internet + wearable device-based home-based multilink prehabilitation management on preoperative functional status and prognosis of patients undergoing VATS surgery compared to the traditional model.

A prospective randomized controlled single-blind clinical trial. 64 patients with diagnosed lung occupations intended for VATS surgery were to be included. They were randomized into the “Internet+” group and the traditional prehabilitation control group.

- 1) Sixty-four adults aged ≤ 75 years; suspected lung cancer intended for VATS lobectomy/sublobar resection were selected for the study.
- 2) Prehabilitation intervention: Both groups underwent individualized home-based multimodal prehabilitation strategies, and the timing of the prehabilitation intervention was about 2 weeks from the time the doctor and the patient jointly decided to have the surgery to 1 day before the surgery. The content of prehabilitation included smoking cessation, aerobic training,

anaerobic exercise, nutritional optimization and psychological support. The "Internet+" group used the management mode of online application + wearable devices; the traditional prehabilitation group used the traditional management mode of preoperative preaching + paper records + regular weekly reminders from medical staff.

- 3) Study endpoints: The follow-up period was from the time when the surgeon and the patient decided to operate to 30 days after the operation. The 6MWD was used as the primary assessment of perioperative functional status and the primary endpoint of the study, and patients were evaluated at enrollment, before surgery, and 30 days after surgery. Secondary endpoints included: length of hospitalization, postoperative complications, and pulmonary function, as well as multiple perioperative functional status scores. The feasibility of "Internet Plus" management and patient implementation were assessed.

4. Sample size and statistical methods

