The design of this study was a prospective randomized controlled study, and the sample size of this study was based on the difference in the primary outcome 6-minute walk test distance (6MWD) between the two groups at 30 days postoperatively. It is currently recognized that a difference of 30m in a patient's 6MWD is clinically significant. According to the pre-test of the research team, the standard deviation of the 6MWD was 40 m. The probability of class I error was calculated as 0.05 bilaterally and $\beta=0.2$ to obtain 29 patients in each of the two groups, and 32 patients in each of the two groups were taken to account for the

10% shedding of medical records.

The statistical software for this study was in R language (R Foundation for Statistical Computing, Vienna, Austria; version 3.5.2). Measurements were expressed as mean \pm standard deviation or quartiles, depending on the distribution, and counts were expressed as frequencies. In this study, for the primary outcome 6MWD, as well as for the WHODAS 2.0, and the HADS psychological scores, repeated measurements were taken at different time points in the same patient. Considering the correlation between multiple measurements, a linear mixed-effects model was developed in this study to analyze the effect of the intervention. Intervention factors, time points as categorical variables, and interactions between intervention factors and time as fixed effects were included in the model. When there was no evidence in the model suggesting an interaction between the intervention and time, it was removed from the model to estimate the effect of the intervention on the primary outcome at all time points and the effect of time on the primary outcome. Also, given the potential bias of patients missing visits, we will perform sensitivity analyses of the worst measurements for all patients with missing 6MWD data and determine whether missing data have an impact on the analysis of the primary outcome. For other single-measure secondary outcomes, group comparisons were performed using the paired t test for measures that satisfied normality and the nonparametric Mann-Whitney U test for measures that did not satisfy normality. Count data were expressed as frequencies, and intergroup comparisons were performed using the χ^2 test. The test level was $\alpha=0.05$. A statistically significant difference was defined as a two-sided $P<0.05$.

5. Patient inclusion and exclusion criteria

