5.1 Inclusion

- 1) Age: 18-75 years;
- 2) 64 adults with suspected lung cancer proposed for VATS lobectomy/sublobar resection.

5.2 exclusion:

- 1) Patient refusal;
- 2) ASA classification III or higher;
- 3) Pre-neoadjuvant chemotherapy;
- 4) Inability to cooperate (psychiatric abnormalities, impaired consciousness, mental retardation);
- 5) Comorbidities cannot tolerate home rehabilitation or functional motor examination;
- 6) Inability to use a smartphone or read Chinese;
- 7) Average weekly moderate-intensity/high-intensity exercise of >90min/>60min.

6. Research process

- 1) Patients were assessed for enrollment criteria at the time of their initial outpatient visit and decision to proceed with surgery. After obtaining informed consent from the patients, basic information (basic, past medical history, metabolic equivalents, etc.), smoking status, ASA classification, metabolic equivalents, 6MWD, lung function, grip strength, NRS 2002 nutritional risk screening, HADS and WHODAS 2.0 scores were collected
- 2) Both groups were given routine preoperative anesthesia clinic visits and

guidance, and a short-term home multimodal prehabilitation intervention strategy of about 2 weeks, including smoking cessation, aerobic exercise, impedance training, respiratory exercise, nutritional guidance, whey protein powder supplementation and psychological support. Elastic bands, whey protein powder and respiratory trainers were distributed to patients in both groups.

The “Internet+” team trained patients on the online application of the “Preoperative Family Prehabilitation Program” . The patients used the online application for prehabilitation, followed the exercises, and used the sports bracelet as a wearable device to adjust the exercise intensity and record the exercise time.

Patients in the traditional group were issued a portable finger oxygenator to assist in the completion of exercises, as well as a Pre-Rehabilitation Manual and Completion Record Form, which patients were instructed to fill out daily, and patients were followed up twice a week.

Comprehensive reference to previous studies and prior research by the group, combined with patient execution, to propose a concise and easy-to-follow exercise program:

- i) Tobacco and alcohol cessation
- ii) Aerobic exercise

Aerobic exercise is the core of exercise training in a way that consists of two steps, the first step being a 5-minute warm-up process. The second

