[figure not shown]
performed twice a day for 10 minutes each time, and respiratory exercises include balloon blowing, three-ball instrument, respiratory trainer, and active cycle breathing techniques. Individualized protocols are developed based on the patient's underlying respiratory function and tolerance.

v) Dietary and psychological adjustments

The European Society of Clinical Nutrition and Metabolism recommends a daily protein intake of 1.2g/kg-1.5g/kg (ideal weight for obese patients) for surgical patients. Patients are advised to change unhealthy dietary habits, especially high-calorie and high-fat diets, and increase the intake of vegetables, fruits and high-quality proteins (fish, chicken breast and other lean meats, milk, eggs, soybeans) as appropriate. In addition, patients are advised to supplement high-quality protein, such as whey protein powder, one hour before exercise every day to better promote muscle synthesis according to their individual conditions. Encourage patients to perform self-psychological adjustment and listen to relaxing music to sleep before bedtime every day.

The 6MWD at 30 days postoperatively was used as the primary assessment of functional status and the primary endpoint of the study (enrollment, preoperative and 30 d postoperative); secondary endpoints included pulmonary function, length of hospital stay, ICU stay, postoperative complications, and hospitalization costs, and the HADS assessed perioperative psychosocial, the QoR-15 scale assessed

near-term prognosis, and the WHODAS-2.0 scale assessed mid-term prognosis.

7. Research quality control

- 1) All 6-minute walk tests were measured by a unified person, conducted in accordance with international standard procedures and equipped with first-aid

medicines, so that patients could be dealt with in a timely manner if they felt unwell or needed to take a rest;

2) The whey protein powder provided free of charge to the patients was selected from "Nerishi" isolate whey protein powder through the Nutrition Department of the hospital, taking into consideration the purity, purification method, safety, taste and other issues;

3) For patients in the traditional prehabilitation group who have no wearable devices, patients are provided with free finger oxygen meters to facilitate patients to record their heart rate during aerobic exercise, adjust the intensity of exercise, and ensure the safety and effectiveness of exercise;

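### Pulmonary function is measured at enrolment, but section 4 gives that value no role in comparing the arms, at a cost in precision

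*Combined protocol and SAP*

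**What the plan says.** All references are to the combined protocol and SAP.

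- **Endpoint status.** Section 3.2, item 3 states: "Secondary endpoints included: length of hospitalization, postoperative complications, and pulmonary function". The endpoint paragraph that closes section 6 repeats it: "secondary endpoints included pulmonary function, length of hospital stay, ICU stay, postoperative complications, and hospitalization costs". Neither place gives the parameter, the unit or the time of the follow-up measurement.
- **Enrolment value.** The assessments at the first outpatient visit (section 6, item 1) include lung function: "6MWD, lung function, grip strength, NRS 2002 nutritional risk screening, HADS and WHODAS 2.0 scores were collected".
- **Repeated-measures analysis.** Section 4 describes the linear mixed model for three outcomes only: "for the primary outcome 6MWD, as well as for the WHODAS 2.0, and the HADS psychological scores, repeated measurements were taken". Pulmonary function is not among them.
- **Everything else that is continuous.** Section 4 continues: "For other single-measure secondary outcomes, group comparisons were performed using" a paired t-test when normality holds, with Mann-Whitney U as the alternative when normality fails. Neither test has a baseline term.

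No section says how the enrolment lung-function value enters the comparison between arms.

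**The concern.** Lung function is recorded before the programme starts. For pulmonary function to serve as an endpoint it must be measured again later, so at least two values per patient are implied. Section 4 has one rule for named repeated measures and one for single measures. Pulmonary function is missing from the first, so it reaches the second only because nothing else is available, and that rule ignores the enrolment value.

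Precision matters here because both arms follow the same programme, including respiratory exercise and respiratory trainers (section 6, item 2). The arms differ in how the programme is delivered and supervised, so a between-arm difference in lung function may well be small. The sample size was set for 6MWD alone. An analysis that leaves out a relevant baseline value already in hand gives a wider interval than necessary, and a chance difference between the arms at enrolment passes into the follow-up comparison uncorrected.

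**Working it through.** **The plan's own figure.** Section 4 gives a 6MWD difference of 30 m, SD 40 m, two-sided alpha 0.05 and beta 0.2.

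- Normal approximation: n = 2 × [40 × (1.960 + 0.842) / 30]² = 27.9, so 28 per arm. The exact two-sample t-test gives 28.9, so 29, as stated.
- Dropout of 10%: 29 × 1.10 = 31.9, so 32, as stated. (Dividing gives 29 / 0.90 = 32.2, so 33; the difference is immaterial here.)

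The plan gives no figure for pulmonary function. I take 29 evaluable patients per arm from the 6MWD calculation and work in units of the follow-up SD.

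**Unadjusted comparison of two independent arms**

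- Standard error = √(2/29) = 0.263 SD.
- 95% half-width = 2.003 × 0.263 = 0.53 SD (t with 56 degrees of freedom).
- Difference detectable with 80% power = 2.802 × 0.263 = 0.74 SD.

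**Adjusted for the enrolment value.** Let r be the correlation between the enrolment and follow-up values. ANCOVA multiplies the variance by 1 − r², so half-width and detectable difference shrink by √(1 − r²), and the equivalent sample size grows by 1/(1 − r²). The single degree of freedom spent on the covariate is ignored as negligible. The documents give no r, so a range is shown.

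| Assumed r | 1 − r² | 95% half-width (SD) | Detectable difference (SD) | Power for an illustrative 0.5 SD | Equivalent multiple of patients |
|---|---|---|---|---|---|
| Unadjusted | 1 | 0.53 | 0.74 | 48% | 1 |
| 0.5 | 0.75 | 0.46 | 0.64 | 59% | 1.3 |
| 0.7 | 0.51 | 0.38 | 0.53 | 76% | 2.0 |
| 0.8 | 0.36 | 0.32 | 0.44 | 89% | 2.8 |
| 0.9 | 0.19 | 0.23 | 0.32 | 99% | 5.3 |

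Detectable differences and powers use the normal approximation.

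**Chance imbalance.** The enrolment difference between arms also has a standard error of 0.263 SD. A one-standard-error imbalance with r = 0.8 would, with equal SDs at the two visits, shift the unadjusted follow-up difference by 0.8 × 0.263 = 0.21 SD. This is the same loss seen another way; it is already contained in the wider unadjusted interval.

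**Why ANCOVA and not a simple change score.** With equal SDs, the change score has variance 2(1 − r). At r = 0.5 that is 1.0, no better than ignoring the enrolment value; at r = 0.7 it is 0.60, against 0.51 for ANCOVA.

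**The case against.** **The plan never calls pulmonary function single-measure.** This is correct. An outcome measured at enrolment and again later fits neither rule literally, so a reader who infers that the plan chose to discard the enrolment value reads a decision into a silence. But if the single-measure rule does not apply, a named secondary endpoint has no stated analysis. Section 4 needs the same repair either way.

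**The rule as printed is not a raw two-arm comparison.** Also correct for normally distributed data: the sentence names a paired t-test, which does not compare two independent arms. That is a separate error in the same sentence. The calculation above assumes it is corrected to an independent-samples test. Read instead as before-versus-after within each arm, it would use the enrolment value but would not compare the randomised groups.

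**A reader might infer that body size, sex and extent of resection dominate the comparison.** The documents do not support this. They give no parameter, unit, SD or correlation, and percent-predicted values would remove much of the influence of size and sex. The enrolment value explains a fraction r² of the follow-up variance, 25% to 81% over the assumed range, and more than half only if r exceeds about 0.71. Extent of resection does vary (section 5.1: "64 adults with suspected lung cancer proposed for VATS lobectomy/sublobar resection"), but it matters only for a postoperative value, and no time point is stated. Adjusting for enrolment lung function would not remove it.

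**Randomisation already protects the comparison.** On average it does, and the test's alpha allows for chance imbalance. What stands is that the interval is wider than it needs to be.

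**The gain depends on r.** It does. At r = 0.5, which is possible for a value taken after lung resection, the gain is a modest 1.3-fold. The cost of adjusting when r is low is about one degree of freedom.

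**Conclusion.** The point holds as a matter of efficiency and specification. The enrolment lung-function value is collected, pulmonary function is a secondary endpoint, and section 4 gives that value no place in the analysis. With 29 patients per arm the 95% half-width is 0.53 SD unadjusted, against 0.46 to 0.23 SD adjusted for assumed correlations of 0.5 to 0.9. These figures rest on three assumptions: 29 evaluable patients per arm for this endpoint, a correlation within that range, and a corrected independent-groups test as the comparator.

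Two stronger readings should be set aside. The omission does not bias the randomised comparison. Nor is this endpoint a test of whether breathing training works: section 6 says such training helps lung function, but both arms receive it, so a between-arm difference can reflect only the app-plus-wearable versus the traditional mode of delivery. The primary endpoint is not affected.

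**What to change.** In section 4:

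1. State the pulmonary function parameter, its unit (for example litres or percent predicted) and the follow-up time point(s).
2. Take pulmonary function out of the single-measure rule. Compare follow-up values between arms by ANCOVA with the enrolment value as covariate. Alternatively, add it to the repeated-measures model with the enrolment value treated as baseline. That proviso is needed because section 4 drops the interaction when there is no evidence for it and then estimates one effect over all time points, which would include enrolment.
3. If a postoperative value is used, planned extent of resection (lobectomy or sublobar) may be added as a covariate. Use the planned extent, not the extent performed, because the latter is fixed after enrolment.
4. Describe the result as an effect of delivery mode, not of training.

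The cost is a wording change, best made before outcome data are examined. The enrolment value is already collected, and no new visit or test is needed.

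The paired t-test in the same sentence should be corrected at the same time.

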5.1 Inclusion

- 1) Age: 18-75 years;
- 2) 64 adults with suspected lung cancer proposed for VATS lobectomy/sublobar resection.

5.2 exclusion:

- 1) Patient refusal;
- 2) ASA classification III or higher;
- 3) Pre-neoadjuvant chemotherapy;
- 4) Inability to cooperate (psychiatric abnormalities, impaired consciousness, mental retardation);
- 5) Comorbidities cannot tolerate home rehabilitation or functional motor examination;
- 6) Inability to use a smartphone or read Chinese;
- 7) Average weekly moderate-intensity/high-intensity exercise of >90min/>60min.

6. Research process

- 1) Patients were assessed for enrollment criteria at the time of their initial outpatient visit and decision to proceed with surgery. After obtaining informed consent from the patients, basic information (basic, past medical history, metabolic equivalents, etc.), smoking status, ASA classification, metabolic equivalents, 6MWD, lung function, grip strength, NRS 2002 nutritional risk screening, HADS and WHODAS 2.0 scores were collected
- 2) Both groups were given routine preoperative anesthesia clinic visits and

guidance, and a short-term home multimodal prehabilitation intervention strategy of about 2 weeks, including smoking cessation, aerobic exercise, impedance training, respiratory exercise, nutritional guidance, whey protein powder supplementation and psychological support. Elastic bands, whey protein powder and respiratory trainers were distributed to patients in both groups.

The “Internet+” team trained patients on the online application of the “Preoperative Family Prehabilitation Program” . The patients used the online application for prehabilitation, followed the exercises, and used the sports bracelet as a wearable device to adjust the exercise intensity and record the exercise time.

Patients in the traditional group were issued a portable finger oxygenator to assist in the completion of exercises, as well as a Pre-Rehabilitation Manual and Completion Record Form, which patients were instructed to fill out daily, and patients were followed up twice a week.

Comprehensive reference to previous studies and prior research by the group, combined with patient execution, to propose a concise and easy-to-follow exercise program:

- i) Tobacco and alcohol cessation
- ii) Aerobic exercise

Aerobic exercise is the core of exercise training in a way that consists of two steps, the first step being a 5-minute warm-up process. The second

step is a 25-minute aerobic exercise in the form of simple popular methods such as brisk walking, jogging, stair climbing, swimming, aerobics or cycling, depending on the patient. The frequency of exercise is at least 3 times a week.

Exercise intensity was evaluated by both rating of perceived exertion (RPE), i.e., Borg score (see table below), and target heart rate. The target heart rate was calculated based on the patient's age, i.e., target heart rate = $(220 - \text{age} - \text{base heart rate}) \times 70\% + \text{base heart rate}$, which could be recorded by finger oxygenator or exercise bracelet. The exercise intensity setting of aerobic exercise should be controlled between 13-16 points of modified Borg score, i.e., subjective exertion is felt as a little bit hard or forceful, and the exercise intensity is appropriately increased if it is felt that the exercise can be easily accomplished, and the intensity of the exercise can be lowered when the self-perception of fatigue is heavy or slightly severe dyspnea is felt, and overly strenuous exercise is not recommended.

Improved Borg Scoring Indicator

Borg score	Self-perceived level of exertion
6-8	Very, very light.
9-10	very light
11-12	light
13-14	A little hard

15-16	hard
17-18	Very hard
19-20	Very, very hard

iii) Anaerobic exercise

Muscle strength training includes all muscle groups needed in daily life (biceps, triceps, deltoids, pectoralis major, latissimus dorsi, obliques, lumbar, abdominal, gluteal, quadriceps, etc.), and the exercises are performed with self-weighted training or resistance bands. Movements can be selected according to the patient's own situation. Resistance bands with appropriate weights are individualized according to the patient's condition. Strength training was done in 3 sets of 10-12 repetitions for each movement. Again the intensity of exercise was evaluated on Borg scale. The duration of anaerobic exercise i.e. strength training was about 10-15 minutes to prevent muscle soreness and affect compliance. The frequency of training was 2 times a week, alternating with aerobic exercise.

iv) Breathing exercise

The prehabilitation program for patients undergoing lung surgery requires emphasis on breathing exercises in addition to exercise workouts. The latter helps to improve lung function, facilitates sputum expulsion, increases lung capacity, and prevents the occurrence of perioperative pulmonary atelectasis. Respiratory function training is recommended to be

[figure not shown]
performed twice a day for 10 minutes each time, and respiratory exercises include balloon blowing, three-ball instrument, respiratory trainer, and active cycle breathing techniques. Individualized protocols are developed based on the patient's underlying respiratory function and tolerance.

v) Dietary and psychological adjustments

The European Society of Clinical Nutrition and Metabolism recommends a daily protein intake of 1.2g/kg-1.5g/kg (ideal weight for obese patients) for surgical patients. Patients are advised to change unhealthy dietary habits, especially high-calorie and high-fat diets, and increase the intake of vegetables, fruits and high-quality proteins (fish, chicken breast and other lean meats, milk, eggs, soybeans) as appropriate. In addition, patients are advised to supplement high-quality protein, such as whey protein powder, one hour before exercise every day to better promote muscle synthesis according to their individual conditions. Encourage patients to perform self-psychological adjustment and listen to relaxing music to sleep before bedtime every day.

The 6MWD at 30 days postoperatively was used as the primary assessment of functional status and the primary endpoint of the study (enrollment, preoperative and 30 d postoperative); secondary endpoints included pulmonary function, length of hospital stay, ICU stay, postoperative complications, and hospitalization costs, and the HADS assessed perioperative psychosocial, the QoR-15 scale assessed

near-term prognosis, and the WHODAS-2.0 scale assessed mid-term prognosis.

7. Research quality control

- 1) All 6-minute walk tests were measured by a unified person, conducted in accordance with international standard procedures and equipped with first-aid

medicines, so that patients could be dealt with in a timely manner if they felt unwell or needed to take a rest;

2) The whey protein powder provided free of charge to the patients was selected from "Nerishi" isolate whey protein powder through the Nutrition Department of the hospital, taking into consideration the purity, purification method, safety, taste and other issues;

3) For patients in the traditional prehabilitation group who have no wearable devices, patients are provided with free finger oxygen meters to facilitate patients to record their heart rate during aerobic exercise, adjust the intensity of exercise, and ensure the safety and effectiveness of exercise;

4) provide patients with free three-ball instrument respiratory trainer, resistance respiratory trainer and elastic band exercise equipment without safety problems.

The three-ball instrument respiratory trainer and our hospital unified sale for the same manufacturer and supplier products;

5) Full-process supervision of patients' prehabilitation implementation, including daily short message reminders and study log-in records for patients in the Internet + wearable device group, and 2 weekly SMS/WeChat or telephone follow-up visits for patients in the traditional group to ensure their implementation;

6) Data are entered by two persons, and data consistency test is conducted to clean and screen the data to avoid entry errors.

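### Planned extent of resection (lobectomy or sublobar) is neither a stated stratification factor nor in the 6MWD model: a cheap gain in precision is forgone, though validity is not at risk.

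*Combined protocol and SAP*

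**What the plan says.** - **Population.** Section 5.1 (Inclusion) admits "64 adults with suspected lung cancer proposed for VATS lobectomy/sublobar resection". Section 3.2 describes the same mix. No quota or expected split between the two operations is given.
- **Endpoint.** Sections 4 and 6 place the primary 6MWD comparison at 30 days after surgery. 6MWD is also measured at enrolment and before surgery.
- **Allocation.** Section 3.2 says only: "They were randomized into the “Internet+” group and the traditional prehabilitation control group". No stratification, blocking or minimisation is described.
- **Model.** Section 4 states: "Intervention factors, time points as categorical variables, and interactions between intervention factors and time as fixed effects were included in the model". Extent is not a term, and no subgroup or sensitivity analysis by extent is planned.
- **Baseline data.** The items listed in section 6, step 1, do not include planned extent.
- **Sample size.** Section 4 takes the view that "a difference of 30m in a patient's 6MWD is clinically significant" and adds: "According to the pre-test of the research team, the standard deviation of the 6MWD was 40 m". It does not say when the pre-test was measured, in whom, or after which operations.

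**The concern.** The two operations remove different amounts of lung, and the primary endpoint is measured after that removal. If recovery of walking distance at 30 days depends on extent, the dependence is a source of outcome variation that the plan neither balances nor models.

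The repeated 6MWD measurements do not solve this. They absorb stable differences between patients, such as fitness at enrolment. A fall caused by the resection comes after both the enrolment and the preoperative visit, so neither carries information about it. For the same reason a single main effect of extent, constant over the three visits, would largely miss it; the term that matters is extent by time.

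At stake is the precision of the 30-day comparison in a small trial designed with almost no power to spare, and how readily the result could be interpreted if the arms happened to differ in their share of lobectomies.

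**Working it through.** **1. The plan's own figure.** Inputs from section 4: difference 30 m, SD 40 m, two-sided alpha 0.05, beta 0.2.
- Two-sample t-test, standardised difference 30/40 = 0.75: n = 28.9, so 29 per arm. The normal approximation gives 28. The stated 29 reproduces.
- Power at 29 per arm: 80.1%.
- Standard error of the difference: 40 × √(2/29) = 10.5 m.
- Allowance for 10% dropout: 29 × 1.10 = 31.9, so 32, as stated (29/0.90 would give 33).

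**2. Chance imbalance in the lobectomy share.** The share p is not in the documents; 50% and 30% are assumed. The number of lobectomies in each arm is taken as binomial(n, p), and the event is a difference of 20 percentage points or more.

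| Patients per arm | Smallest count difference | p = 50% | p = 30% |
|---|---|---|---|
| 32 (randomised) | 7 (7/32 = 21.9 points) | 10.3% | 7.5% |
| 29 (evaluable) | 6 (6/29 = 20.7 points) | 14.8% | 11.4% |

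Part of the difference between the rows comes from the whole-number threshold.

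With an extent gap of D metres, a 20-point imbalance moves the estimate by 0.20 × D. That is 2, 4, 6 or 8 m for D = 10, 20, 30 or 40 m, or about 0.2, 0.4, 0.6 or 0.8 of the 10.5 m standard error.

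**3. What modelling extent could recover.** D is not in the documents and is assumed. Take the 40 m SD as already including the surgical mix, and the modelled extent as the one performed. The variance due to extent is p(1 − p)D², and the residual SD is √(40² − p(1 − p)D²). At p = 50%:

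| D (m) | Extent variance (m²) | Share of 1600 | Residual SD (m) | Power for 30 m, 29 per arm |
|---|---|---|---|---|
| 0 | 0 | 0% | 40.0 | 80.1% |
| 10 | 25 | 1.6% | 39.7 | 80.8% |
| 20 | 100 | 6.3% | 38.7 | 82.6% |
| 30 | 225 | 14.1% | 37.1 | 85.7% |
| 40 | 400 | 25.0% | 34.6 | 90.0% |

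A 50% share maximises the gain. At p = 30% and D = 30 m, the residual SD is √(1600 − 189) = 37.6 m and power is 84.8%.

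**4. If plan and operation differ.** Suppose the gap by planned extent is 70% of a true 30 m gap, that is 21 m. Then p(1 − p)D² = 0.25 × 441 = 110 m², the residual SD is 38.6 m, and power is 82.9% instead of 85.7%.

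**5. If 40 m is instead the SD within one type of operation.** The pooled SD at p = 50% and D = 30 m is √(1600 + 225) = 42.7 m. Unadjusted power at 29 per arm is then 74.8%, and 33 evaluable per arm would be needed for 80%. The documents do not show which reading of the SD applies.

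All powers are for a two-sample t-test at day 30, the basis on which the 29 reproduces, and not for the three-visit mixed model.

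**The case against.** The strongest reply is that leaving one prognostic factor out of a 64-patient trial is common and valid. Type I error is not inflated, and the sample size arithmetic is sound. If the pre-test sample had the same surgical mix and was measured after surgery, the 80% power already carries this variation and nothing promised has been lost. The gap is also wholly assumed: at 10 m the gain is under one percentage point of power. All of this stands, and it limits the point to an improvement in precision.

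Three stronger readings are tempting, and the documents do not support them.

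- **That the 30-day comparison is biased or confounded by extent.** Allocation is randomised, so the estimate is unbiased over repetitions, and chance imbalance in extent is among the things the unadjusted standard error covers. In a single trial an imbalance can push the estimate either way, but by less than one standard error in the cases shown.
- **That the intended operation is already known for each patient because it is an eligibility criterion.** The criterion is met by either operation. It does not show that a choice between them has been made, or recorded, before randomisation.
- **That the trial is underpowered.** That would follow only if the 40 m SD excluded the surgical mix, which the documents neither say nor rule out.

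The absence of stratification is inferred from silence in the design and statistics sections. If a stratified list exists, the plan should say so and carry the factor into the model.

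**Conclusion.** The point holds as a cheap improvement in precision. Both extents are enrolled, the primary measurement follows the resection, and extent is neither a stated stratification factor nor a model term. Variation in 30-day 6MWD that depends on extent therefore stays in the error term, where the earlier 6MWD values cannot reach it.

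Its size is unknown because the plan gives neither the lobectomy share nor the gap. On the assumptions in step 3 of the working, the gain runs from under 1 point of power (10 m gap) to about 10 points (40 m gap). It is modest up to 20 m and becomes material from about 30 m. A lobectomy share away from 50%, or a plan that often changes, makes it smaller. An imbalance of 20 points or more among those randomised is possible but not likely, at about 8% to 10%; in the evaluable set it is 11% to 15%.

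**What to change.** 1. Record the planned extent (lobectomy or sublobar) for every patient before randomisation, as a named baseline item.
2. If randomisation has not begun, stratify the allocation on it.
3. Prespecify planned extent and planned extent by time as fixed effects in the 6MWD mixed model. Use planned rather than performed extent, because the operation performed is settled after randomisation.
4. State the population, time point and surgical mix behind the 40 m SD, so that a reader can tell whether the sample size already allows for this variation.

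The cost is one extra baseline item, two allocation lists in place of one, and a few degrees of freedom. If enrolment is under way, steps 1 and 3 can still be done before analysis, provided the plan as it stood before randomisation can be recovered from the records. The return is small if the gap is small or the plan often changes.
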